4.4 Safety endpoint(s)

The safety endpoints of this study are:

1. Frequency, severity and causal relationship of AEs, Serious Adverse Events (SAEs) and Adverse Events of Special Interest (AESIs) during the entire study period.
2. Antibody formation, evaluation pre-dose before each treatment, at four weeks after each treatment and at the final study visit.
3. Safety assessments by evaluating hematology, clinical chemistry, vital signs and ECGs as per study schedule.

Statistical Analysis Plan (SAP)

5 SAMPLE SIZE AND POWER

The primary endpoint is a composite endpoint comprising investigator and subject assessments of treatment effectiveness using the FWS. The FWS in this study corresponds to the FWS Investigator assessment (GLS-I) and the FWS for Subject self-assessment (GLS-S). Composite endpoint treatment success (CETS) is defined as ≥ 2 point reduction in FWS score at maximum frown achieving a score of 0 or 1 at the visit week 4 relative to baseline based on investigator assessment and subject assessment. Thus, a subject is a CETS “responder” only if both investigator- and subject-rated success criteria are satisfied at the visit 4 weeks after baseline.

The primary analysis of efficacy is the proportion of responders in the BoNT/A-DP treatment group compared with the placebo treatment group. For superiority testing of BoNT/A-DP compared with placebo, the following assumptions for the sample size calculation are used:

Statistical Analysis Plan (SAP)

Item	Assumption	Comments
Underlying test	Fisher's Exact Test	Standard test for a response parameter for small numbers
Randomization scheme	3:1	More active treatment subjects to enlarge safety data base
Power 1- β	90%	
Significance level (α)	0.025 one-sided	
Response Arm BoNT/A-DP	60%	From the range of observed response rates, a more conservative value of 60% has been chosen
Response Arm Placebo	10%	Conservative value
Software		The sample size calculation was performed using the software nQuery Advisor® 7.0.

Based on these assumptions, 42 subjects in the BoNT/A-DP arm and 14 subjects in the placebo arm are required, i.e. 56 subjects in total. This is a very small sample size and not sufficient for a detailed evaluation of the data, including subgroup analyses. Furthermore, the response rate could not be estimated with sufficient precision. A two-sided confidence interval (CI) of 95%, and a distance from the CI limit of about 4.5% could be achieved with a sample size of 450 subjects in the BoNT/A-DP group. Therefore, a 3:1 randomization of BoNT/A-DP (525 subjects) to placebo (175 subjects) was proposed, which should be adequate for a precise estimate of response rate and for post-hoc sensitivity analyses (i.e. treatment-by-center and other subgroup analyses), also taking into account a drop-out rate.

In total, 700 evaluable subjects will be enrolled. Applying a 10% drop out rate would result in a total number of about 630 subjects.

Statistical Analysis Plan (SAP)

6 ANALYSIS POPULATIONS

6.1 Safety Analysis Set (SAF)

All subjects who received at least one injection with study medication (independent of whether it is BoNT/A-DP or placebo) will be valid for the SAF. Within the SAF, a subject will be considered for the treatment actually received and not for the treatment assigned by randomization, if different. The SAF will be used for the evaluation of the safety assessments and for the individual subject data listings.

6.2 Full Analysis Set (FAS)

The FAS includes all randomized subjects who received at least one injection with study medication (independent of whether it is BoNT/A-DP or placebo). Within the FAS, a subject will be considered for the treatment assigned by randomization and not for the treatment actually received, if different, i.e. following the intent-to-treat (ITT) principle. The FAS will be used for the evaluation of the efficacy assessments. The FAS serves as the primary efficacy analysis set.

6.3 Modified Full Analysis Set (MFAS)

The MFAS includes all subjects included in the FAS who had a baseline (visit 1 at day 0) and at least one post-dose in-clinic assessment with the FWS by either the investigator or the subject on visits at weeks 1, 2 or 4. Within the MFAS, a subject will be considered for the treatment assigned by randomization and not for the treatment actually received, if different, i.e. following the ITT principle. The MFAS will be used for the evaluation of the efficacy assessments.

6.4 Per-Protocol Analysis Set (PP)

The PP includes all subjects who had no significant protocol deviations and an in-clinic assessment with the FWS by the investigator and the subject at baseline (day 0) and at the week 4 visit. For the PP, all subjects will be assigned to the treatment actually received. The PP will only be analyzed for main efficacy outcome measures.

Statistical Analysis Plan (SAP)

6.5 Protocol deviations and exclusions from analysis sets

All protocol deviations and exclusions of subjects from analysis sets will be identified at the Data Review Meeting (DRM) just prior to study unblinding.

Deviations from protocol will be classified as major or minor.

The following protocol deviations are considered to be major and will lead to exclusion from the PP:

- Subject or investigator unblinded to treatment
- Improper storage of IMP and IMP temperature excursion without proper notice to the CRA
- Incorrect treatment allocation or dose
- Wrong injection points used.
- Site staff performing the study assessment not trained

6.6 DRM

For the DRM appropriate listings displaying all relevant data will be provided to the sponsor and serve as a source for the protocol deviations discussion about the classification into major and minor. No unblinding will be done for creation of these listings.

The following protocol deviations will be assessed on a case-by-case basis and a final decision on a possible exclusion from the PP will be done during the DRM:

- Inclusion/exclusion criteria violated
- Use of disallowed medications
- Serious breach of GCP
- Photography not collected or available for all visits
- Site staff performing the study assessment not trained
- Failure to discontinue subjects where appropriate.
- Subject re-treated despite not meeting all re-treatment eligibility criteria

Patients with minor protocol deviations will not be excluded from the PP.

Statistical Analysis Plan (SAP)

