9.5 Subject Completion/Discontinuation

A subject is considered to have completed the study when he/she ceases active participation in the study because the subject has, or is presumed to have, followed all appropriate conditions of a protocol (with or without protocol deviations). Completion of the first cycle and the open label cycles will be documented on two different CRF pages.

Subjects will be considered to be "per protocol completers" of Cycle 1 if they had no significant protocol deviations **in the first cycle** and an in-clinic assessment with the FWS by the investigator and the subject at baseline (day 0) and at the week 4 visit were performed.

Subjects will be considered to be "per protocol completers" of the study if they have completed the final cycle within week 48-60, without significant protocol deviation.

Reasons for completion or non-completion will be reported on the Completion/Termination CRF, including: completed, screen failure, premature termination due to AE (including death), discontinuation by subject (e.g. dropout, lost to follow-up, withdrawn informed consent), physician decision (e.g. non-compliance with protocol, or for safety reasons), study terminated by Sponsor, or other reason to be specified by the investigator. Regardless of the reason for subject withdrawal, all data available for the subject up to the time of completion/discontinuation should be transferred from the subject records on the appropriate CRF.

Every effort will be made to have discontinued subjects complete the End of Study visit. All procedure and assessment results performed at such visits will be recorded under the Termination visit assessments. If a subject terminates participation in the study during or after a visit and does not return for a Completion/Termination visit, their last recorded assessments shall remain under the last visit they attended (i.e. no assessment data shall be recorded under/transferred to the Completion/Termination visit assessments). The reason for discontinuation will be recorded on the CRF.

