8.6.2 Analysis of primary efficacy endpoint(s)

Primary Analysis:

The proportion of subjects (responders) meeting the primary endpoint with a FWS score of 0 or 1 and an improvement ≥ 2 points in FWS score (at maximum frown) at week 4 visit relative to baseline, based on both the investigator and the subject in-clinic assessments will be analyzed using the Cochran-Mantel-Haenszel test with stratification variable site using a significance level (α) of 0.025. Small sites with less than 3 placebo subjects will be combined. The null hypothesis H_0 given below will be tested against the alternative hypothesis H_1 :

$$H_0: p_{BoNT/A-DP} \leq p_{Placebo}$$

$$H_1: p_{BoNT/A-DP} > p_{Placebo}$$

The Cochran-Mantel-Haenszel test will be applied by the SAS procedure Proc Freq using the General Association Statistic. The one-sided p-value will be derived by halving the two-sided p-value delivered by the SAS procedure. Superiority of BoNT/A-DP over placebo will only be concluded if, besides statistical significance (one-sided p-value

Statistical Analysis Plan (SAP)

≤ 0.025), the proportion of responders in the BoNT/A-DP treatment group is higher than for the placebo treatment group.

The FAS will serve as the primary analysis set.

Subjects with missing investigator or subject in-clinic assessments with the FWS at baseline or visit week 4 will be assigned as being non-responders.

Additional Exploratory Analyses on the Primary Endpoint Variable:

Further analyses on the primary endpoint variable are exploratory. A one-sided Pearson χ^2 -test will be applied. Two-sided CI of 95% for the responder rates in the BoNT/A-DP and the placebo treatment groups will be calculated using Wilson scores. As a sensitivity analysis for the primary endpoint, a tipping point analysis will be performed. Each missing value will be assigned to either a response or non-response, so that all possible combinations of replacing one or more missing values within each treatment group will be analyzed. P-values will be calculated for each combination and graphically displayed using a scatter plot.

The CIs will also be calculated for the additional analyses as listed in the following:

- The primary endpoint measure using the observed values only, i.e. missing investigator or the subject in-clinic assessments with the FWS at baseline or week 4 visit will be excluded from analysis but not assigned as being non-responders. This analysis will be performed for the FAS, MFAS and PP populations.

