- The primary endpoint measure using the MFAS and the PP.
- The primary endpoint measure applying the LOCF for week 4 visit. This analysis will be done for FAS, MFAS and PP populations.

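### The SAP puts no cycle limit on per-protocol exclusions, so membership of the week 4 PP set can depend on open-label events; separately, one deviation is listed under two conflicting rules

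*SAP*

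**What the plan says.** SAP 6.4 defines the set: "The PP includes all subjects who had no significant protocol deviations". The section also requires FWS ratings from both raters at day 0 and week 4. It names no cycle and no cut-off date, and adds "The PP will only be analyzed for main efficacy outcome measures". Protocol 12.2 has the same definition and leaves the PP criteria to the SAP.

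SAP 6.5 lists five deviations that exclude automatically: unblinding, improper IMP storage, incorrect allocation or dose, wrong injection points, and "Site staff performing the study assessment not trained". SAP 6.6 lists seven that are judged case by case at the data review meeting (DRM). These include the untrained-staff item again, and "Subject re-treated despite not meeting all re-treatment eligibility criteria".

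The PP set is used for the primary endpoint in SAP 8.6.2 ("The primary endpoint measure using the MFAS and the PP"). SAP 8.6.3 extends the same analyses to the key secondary responder endpoints and repeats the week 4 questionnaire analyses on the PP. All of these are cycle 1 endpoints.

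Protocol 9.5 calls a subject a per-protocol completer "of Cycle 1 if they had no significant protocol deviations" and then limits those deviations to the first cycle. It carries the same baseline and week 4 FWS requirement as the PP, and it defines whole-study completers separately. SAP section 9 lists two changes from the protocol (the safety set and the antibody analysis) and none concerning the PP.

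**The concern.** A per-protocol analysis of week 4 should ask who was treated and assessed as planned up to week 4. Under the SAP wording, a subject with a clean first cycle and a valid week 4 assessment can be removed because of something that happened at a later open-label injection. That is selection on a post-outcome event.

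The selection need not be neutral. Re-treatment requires an FWS score of 2 or 3 from both raters (Protocol 7.3). Placebo-first subjects and active-arm non-responders can therefore be expected to re-treat sooner, and to have more treatments at which a deviation could be recorded. The exclusion rate could then differ by arm and by week 4 response.

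The untrained-staff item is a separate defect. An automatic rule and a discretionary rule cannot both be followed for the same deviation.

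**Working it through.** **Timing of the grounds.** The plan states no figure on this point, so the check starts from the text.

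- Re-treatment is evaluated from week 12 and given no later than week 48 (SAP 3.3).
- A re-treatment deviation therefore falls 12 − 4 = 8 to 48 − 4 = 44 weeks after the week 4 assessment.
- Incorrect dose and wrong injection points can arise at any of up to four treatments. Treatments 2 to 4 fall in the same week 12 to 48 range. Improper storage of the vial for one of those treatments belongs with them.
- Exclusions are settled at a single DRM just before unblinding (SAP 6.5), and analysis follows lock of all data to the end of study (SAP 8.1). Open-label deviations are thus in view when PP membership is decided.

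**Overlap of the lists.** Of the five items in SAP 6.5 and the seven in SAP 6.6, exactly one is common: untrained assessment staff.

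**Size of exclusion.** Assume a 2% chance of an excluding deviation per treatment, with every such deviation leading to exclusion. The documents give no rate. With k treatments the chance of exclusion is 1 − 0.98^k:

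| Treatments counted | Excluded |
|---|---|
| 1 (cycle 1 only) | 2.0% |
| 3 | 5.9% |
| 4 | 7.8% |

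**Difference between arms.** This depends on how many treatments each arm receives. The simulation used these rules:

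- duration of effect is normal, and an active cycle ends at the first 4-weekly visit, from week 12, on or after the effect has ended;
- placebo-first subjects re-treat at week 12;
- there is a cap of four treatments and a week 48 cut-off, with no dropout.

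| Duration | Active-first, mean treatments | Placebo-first, mean treatments | Difference | Difference in exclusion at 2% |
|---|---|---|---|---|
| 17.1 ± 6.5 weeks (Protocol 4.5.1.2) | 3.10 | 3.47 | 0.37 | about 0.7 points |
| Median 12 weeks, SD 5 (SD assumed) | 3.78 | 3.92 | 0.14 | about 0.3 points |

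For the first row, putting in the mean counts: 1 − 0.98^3.10 = 6.1% and 1 − 0.98^3.47 = 6.8%. Subtracting the 2.0% from cycle 1, about 4.1 and 4.8 points of exclusion come from the open-label phase.

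**Bounds on the PP response rate.** Take the planning values of 525 active subjects at 60% response (315 responders; SAP section 5), and suppose a fraction e of them is excluded for late deviations. The rate becomes 315/[525(1 − e)] if all those excluded are non-responders, and (315 − 525e)/[525(1 − e)] if all are responders.

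| e (assumed) | All non-responders | All responders |
|---|---|---|
| 2% | 61.2% | 59.2% |
| 5% | 63.2% | 57.9% |
| 10% | 66.7% | 55.6% |

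These are extremes, not expectations.

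**The case against.** The strongest reply is that little turns on this. SAP 8.6.2 says "The FAS will serve as the primary analysis set", SAP 8.6.1.1 makes analyses in other populations exploratory, and the DRM works before unblinding from listings prepared blind. All of that stands. Blinded review does not remove the selection, however, if the number of treatments is itself related to response.

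A second reply is that Protocol 9.5 already supplies the cycle 1 limit and that no departure is declared. But 9.5 defines completers and does not name the PP set. Protocol 12.2 leaves the PP criteria to the SAP, and the SAP does not repeat the limit. Protocol 12.2 also sends deviation decisions to a classification meeting documented outside the SAP. That meeting might apply the limit, but nothing available says that it will.

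A third reply is that the re-treatment item has a proper use. Protocol 12.4.2 bases the additional secondary endpoints on the PP as well, including endpoint 11, response 4 weeks after re-treatment. This is correct, and it is a reason to assign the item to that endpoint rather than delete it.

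Stronger readings are tempting and should be resisted:

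- A reader might infer that week 4 membership does depend on later events. The re-treatment item is only a possible exclusion, and the DRM may judge it irrelevant to week 4. The automatic items apply only if such a deviation occurs.
- A reader might infer a reach to week 60, or 56 weeks after the outcome. No exclusion rule names week 60, and deviations tied to an injection end at week 48.
- A reader might suppose one extra treatment for placebo-first subjects and a gap of about 2 points. With placebo re-treating at week 12 and every active cycle lasting 12, 16, 20 or 24 weeks, the two arms receive equal counts (4/4, 4/4, 3/3, 3/3). With the cited spread the excess is 0.37.
- A reader might link the duplicated item to the post-outcome problem. It does not cause it.

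**Conclusion.** The point holds in limited form. As written, SAP 6.4 to 6.6 allow, and for the automatic items require, removal of subjects from a week 4 analysis because of open-label deviations. This departs from the first-cycle limit in Protocol 9.5 without being declared in SAP section 9. The two rules for untrained assessment staff contradict each other.

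The effect is confined to the exploratory PP analyses; the FAS primary test is untouched. The between-arm difference in exclusion is about 0.7 points, or about 0.3 points with a 12-week median. Both figures rest on the assumed 2% rate, on certain exclusion for each deviation, and on the simulation rules above. They scale roughly in proportion to the assumed rate. A bias in the estimated response rates has not been demonstrated; the bounds show only how far they could move.

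**What to change.** In SAP 6.4 to 6.6:

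1. State that PP membership for cycle 1 endpoints uses only deviations in cycle 1 up to the visit analysed, consistent with Protocol 9.5.
2. Apply the re-treatment eligibility item and other open-label deviations only to the PP analysis of endpoint 11.
3. Keep the untrained-staff item on one list only.

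One consequence should be confirmed in the text. SAP 8.6.3 counts subjects re-treated before week 16 or week 20 as non-responders at that visit. Under this rule, a subject whose first re-treatment was given outside the criteria stays in the PP as a non-responder for those two endpoints.

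The cost is SAP wording before unblinding. No new data are needed, and the sample size and the confirmatory tests do not change.

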7 STATISTICAL CONSIDERATIONS AND ANALYSIS

7.1 Derived Variables

The below, table provide the list of derived variables for various duration derivations and baseline derivations applicable for this study.

Variables	Formula
Derivation of Duration	
Study day at any visit	Date of interest – date of first dose of study drug.
Extent of Exposure (Days)	Date of last study medication administration – Date of first study medication administration + 1
Extent of Exposure (Weeks)	Extent of exposure (days)/7
Baseline Derivations	
Baseline	The baseline value is defined as the last observation before treatment, i.e. pre-treatment values measured on the treatment day (baseline visit, day 0), and if missing or not evaluated, the value from screening visit.
Change from baseline	Post baseline value – Baseline value
Relative change from baseline	[(Post baseline value – Baseline value)/Baseline value]*100

7.2 Handling of missing data

7.2.1 Missing data analysis methods

Analyses will be performed by visit. For responder analyses on visits at week 4 and week 12, missing in-clinic assessments (investigator or the subject) with the FWS at baseline or week 4 and week 12 visits will be assigned as being non-responders.

As sensitivity analyses, the following additional approaches for handling of missing values will be applied:

- Analysis on observed values only, i.e. missing values will be excluded from analysis.
- Last observation carried forward (LOCF)
- Tipping point analysis: each missing value will be assigned to either a response or non-response, so that all possible combinations of replacing one or more missing

Statistical Analysis Plan (SAP)

values within each treatment group will be analyzed. p-values will be calculated for each combination and graphically displayed using a scatter plot.

The analysis of the week 16 visit regarding the endpoint ‘percentage of responders at week 16 (after first treatment)’ will be conducted on observed values only, i.e. missing investigator or the subject in-clinic assessments with the FWS at baseline or week 16 visit will be excluded from analysis but not assigned as being non-responders. The same approach holds for the endpoint ‘percentage of responders at week 20 or later (after first treatment)’ respectively.

All analyses of the modified Skindex-16 (GL-QoL) Emotional and Functioning domain and overall scores will be conducted on observed values only, i.e. missing domain and overall scores will be excluded from analysis; no imputation of missing domain and overall scores will be performed. The same approach will be followed for the analyses of the FACE-Q scales.

The analysis of “responder” 4 weeks after re-treatment will be conducted on observed values only, i.e. subjects with missing investigator or the subject in-clinic assessments on FWS week 4 or at the preceding end of the cycle visit will be excluded from analysis.

7.2.2 Handling of missing or incomplete dates

7.2.2.1 Imputation rules for missing or partial AE start date:

If only Day of AE start date is missing:

If the AE start year and month are the same as that for the first dose date, then:

- If the full (or partial) AE end date is NOT before the first dose date or AE end date is missing, then impute the AE start day as the day of first dose date.
- Otherwise, impute the AE start day as 1.

Otherwise, if the AE start year and month are not the same as that for the first dose date, then impute the AE start day as 1.

Compare the imputed AE start date with treatment period to determine whether the AE is pre-treatment AE or treatment emergent adverse event (TEAE).

If only Day and Month of AE start date are missing:

If AE start year = first dose year, then:

- If the full (or partial) AE end date is NOT before the first dose date or AE end date is missing, then impute the AE start Month and Day as the Month and Day of first dose date;

- Otherwise, impute the AE start Month as January and the AE start Day as 1.

Otherwise, if AE start year not equal first dose year, then impute the AE start Month as January and the AE start Day as 1.

Compare the imputed AE start date with treatment period to determine whether the AE is pre-treatment AE or TEAE.

If Year of AE start date is missing:

If the year of AE start is missing or AE start date is completely missing then query site with no imputation. Also compare the full (or partial) AE end date to the first dose date. If the AE end date is before the first dose date then the AE should be considered as a pre-treatment AE. Otherwise, the AE will be considered as TEAE.

